4.3 Patient Withdrawal and Replacement

Patients may withdraw from any part of the study at any time without penalty and for any reason without prejudice to his or her future medical care. The Investigator will advise the Sponsor of the withdrawal of any patient.

Patients must be withdrawn from study drug under the following circumstances:

- Patient voluntarily withdraws from study participation;
- Disease recurrence;
- Ineffective treatment;
- Unacceptable toxicity;
- Patient's withdrawal of consent;
- Death;
- Pregnancy (refer to section 6.3.1.11)
- Significant protocol deviation;
- Lost to follow-up;
- If deemed by the Investigator that it is not in the patient's interest to continue with the study.

Withdraws from study participation (follow-up permitted):

Patients withdrawing from the study drug will be encouraged where possible to return to the site for a study follow-up visit, in particular for safety evaluations, study assessments and survival follow-up.

Disease recurrence:

Sites should continue to perform efficacy assessments for patients achieving CR or CRi until disease recurrence (or death in the absence of recurrence) in accordance with IWG criteria for AML. Patients will be withdrawn from the treatment if there is evidence of disease recurrence as defined by IWG Criteria¹⁶ (Cheson, 2003).

Ineffective treatment:

The study drug may be discontinued in the event of:

- Treatment failure (in patients who do not achieve a PR or above after 4 cycles of treatment)
- Relapse, as defined by the IWG Response criteria (for patients with a CR or CRi)
- No longer meeting the criteria for a PR (in patients who were previously determined to have a PR)

Once ineffective treatment has been established, as described above, no further efficacy assessments are required.

Unacceptable toxicity:

If the symptoms are not controlled with standard treatments and are considered to be clinically significant, study drug will be stopped and the patient will be withdrawn from the study drug. Patients removed from study drug for unacceptable toxicity will be followed until resolution or stabilization of the AE.

Patients with a response (CR or CRi) withdrawn from the treatment prior to disease relapse should continue to be followed until the relapse in accordance with the study plan.

Consent Withdrawal:

Patients may withdraw from the study at any time at their own request. The withdrawal of consent should be explained in detail in the medical records by the Investigator and entered in the appropriate electronic case report form (eCRF) page. Details of withdrawal should indicate whether the withdrawal is from further treatment with the study drug only or also from the study procedures and/or post treatment study follow-up. CR or CRi patients who request to withdraw from further treatment and study procedures may be followed up for survival status (if consented by the patients). Similarly, CR or CRi patients who withdraw from treatment only should continue to be followed until disease relapse.

Lost to follow-up:

If a patient does not return for a scheduled visit, every effort should be made to contact the patient to reschedule the visit, by phone, e-mail, text message, and if necessary, by letter and/or certified mail, in instances where the patient is not responsive to contact attempts. On a case-by-case basis, a patient visit should be arranged. All efforts should be documented in the patient's medical source record. A patient is considered lost to follow-up if the patient cannot be reached after 3 months from the scheduled visit or before the date of data cut-off date, whichever is earlier. However, if the patient re-initiates

contact beyond 3 months, or the site is informed of the patient's survival status or date of death, the available data may still be collected on the eCRF, assuming that patient consent has not been withdrawn.

All patients who are withdrawn or discontinued from the study are required to complete a safety follow-up visit within 28 days after the last administration of study drug, where possible. If the Investigator is unable to complete the safety follow-up visit assessments, the reason(s) must be recorded in the eCRF. All AEs/SAEs will be collected until 28 days after the last administration of study drug.

If a patient discontinues study drug and is withdrawn from the study for any reason, the study center must immediately notify the medical monitor. The Investigator should also ensure the return of unused study drug.

Patient Replacement:

As a general principle, patients will not be replaced if they withdraw following the completion of Cycle 1.

4.4 Planned Sample Size and Number of Study Centers

Part 1:

It is planned to recruit up to a total of 18-24 patients across multiple centers in Australia, Singapore and other countries.

Part 2:

It is planned to recruit a total of 20 patients across multiple centers in Australia, Singapore and other countries.

4.5 Patient Identification and Allocation of Treatment

At Screening, each patient will receive a unique Screening number from electronic data capture system (EDC). The number will start with "S" and be followed by 4 digits starting with S0001 for Part 1 and S2001 for Part 2.

Part 1:

Following confirmation of eligibility, all patients will be sequentially assigned to the dose cohorts after being screened for eligibility and providing consent. At administration of the first dose of study drug, patients will be assigned with a 4-digit patient number in the order in which they are enrolled in the study starting from 0001.

Enrolled patients who drop out of the study before receiving the study drug will retain their Screening number.

Part 2:

Following confirmation of eligibility and providing consent, all patients will be sequentially assigned to the dose level selected from Part 1. At administration of the first dose of study drug, patients will be assigned with a 4-digit patient number in the order in which they are enrolled in the study starting from 2001.

Enrolled patients who drop out of the study before receiving the study drug will retain their Screening number.

5 INVESTIGATIONAL PRODUCT

5.1 Identity of Investigational Product

The investigational product for this study is ASLAN003.

ASLAN003 is supplied as a formulated orange-colored hard gelatin capsule (Size No. 2). Each capsule contains ASLAN003 drug substance 50 mg, lactose monohydrate, colloidal silicon dioxide and sodium stearyl fumarate.

5.2 Study Drug Administration

ASLAN003 will be supplied by ASLAN Pharmaceuticals Pte. Ltd. The study drug is to be administered orally, QD or BID. It is recommended to administer the study drug with food or within 30 minutes after food intake.

5.3 Permitted Dose Interruptions of Study Drug

If patients experience a CTCAE Grade ≥ 3 toxicity attributed to ASLAN003 by the investigator, the study drug should be interrupted. Patients with Grade ≥ 3 AEs which are associated with underlying disease such as anemia, bone marrow hypocellular, febrile neutropenia, and decreased lymphocyte count, neutrophil count, and platelet count may keep receiving ASLAN003 treatment at investigator's discretion. The study drug should be resumed once the AE recovers to Grade 1 or less. If study drug is interrupted for continuous 28 days due to AE, the patient must be withdrawn from the study drug and recorded as unacceptable toxicity. If upon re-introduction of ASLAN003, a Grade 2 AE of the same event re-occurs, a dose reduction on a case-by-case basis can be implemented upon agreement with the CRO/Sponsor. For Grade ≥ 3 AST, ALT, or GGT elevations, interruption of study drug is based on the assessment of Child-Pugh score (Class A, B or C, refer to Appendix 3) and is demonstrated in Table 2.

Table 2

If Grade 3 AST/ALT/GGT	
Class A: Reduce dose by 50 mg for 1 week then reassess	G4 : Refer to "If Grade G4 AST/ALT/GGT"
	*Class A, still G3: Reduce dose by 50 mg
	*Class A, G2: Maintain current dose
	*Class A, \leq G1: Resume last higher dose
Class B with Grade 1 to 3: Refer to the action of "If Grade 3 AST/ALT/GGT, Class \leq B"	
Class \geq B: Interrupt until \leq G1, then resume original or reduced dose per investigator's discretion	
If Grade 4 AST/ALT/GGT	
Dose interruption, and follow up weekly until \leq G1	Class A: Reduce dose by 50 mg or maintain original dose per investigator's discretion [#]

	Class \geq B Reduce dose by 50 mg [#]
--	---

*Monitor dose every week until back to original dose

[#]Withdrawal if a secondary G4 event is observed

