The t_{max} and $t_{1/2}$ for ASLAN003 were dose-independent following QD doses across the selected dose range; 5 and 16 hours, respectively. Steady-state concentrations of ASLAN003, LAS186558, and LAS186876 were achieved by Day 4 across the selected dose range. Following daily repeated dosing, exposure to ASLAN003 and LAS186558 (AUC) appeared to accumulate slightly (less than 30% increase). The exposure was higher in elderly subjects (AUC_{tau}) of ASLAN003 was increased by 53% and C_{max} by 41%), which may be explained by their lower body weight. Renal elimination of free (unconjugated) ASLAN003, LAS186558, and LAS186876 were negligible (<0.8% of the administered dose). Phase II metabolism appeared to be an important route of elimination. Conjugation was most prevalent for ASLAN003 and LAS186558.

Most frequently reported adverse events (AEs) across this ASLAN003-001 study were abnormality in laboratory investigations and included elevated alanine aminotransferase (ALT), aspartate aminotransferase (AST), gamma glutamyltransferase, blood cholesterol increased, blood creatine phosphokinase increased, electrocardiogram (ECG) PR, and blood glucose increased. The safety assessment results reported in patients aged ≥ 55 years were mostly comparable with those of younger subjects other than for greater changes in the laboratory assessments in the elderly subjects compared to the younger subjects, notably the liver function tests.

Another Phase IB study (*Study ASLAN003-002*) evaluated the safety, tolerability and PKs of multiple doses of 100 mg of ASLAN003 QD for 14 days in healthy elderly Asian subjects (age > 55 years old). The study was conducted at a single center in Singapore where 7 of the planned 8 elderly subjects were enrolled into Stage 1 of the study, of which

5 subjects received ASLAN 100 mg QD on Day 1; and 4 of these subjects received ASLAN 100 mg QD on Day 8. Only 1 subject completed 14 days of QD dosing. Stage 2 of the study was not conducted. Following daily repeated dosing, mean plasma exposure to ASLAN003 expressed as $AUC_{(0-24)}$ increased 1.2-fold after multiple dosing on Day 8 compared to a single dose on Day 1. Following repeat QD dosing, the relative systemic exposures to the metabolites LAS186558 and LAS186876 were around 10% and 1%, respectively.

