11.3 Appendix 3: Child-Pugh Score

Measure	1 point	2 points	3 points
Total bilirubin, mg/dL	<2	2–3	>3
Serum albumin, g/dL	>3.5	2.8–3.5	<2.8
Prothrombin time, INR	<1.7	1.7–2.3	>2.3
Ascites	Absent	Slight	Moderate
Hepatic encephalopathy	None	Grade I–II	Grade III–IV
Child-Turcotte-Pugh (CTP) Class obtained by adding score for each parameter (total points) Class A: 5-6 points Class B: 7-9 points Class C: 10-15 points			

Kasper, Dennis L., et al. Harrison's Principles of Internal Medicine. 19th edition. New York: McGraw Hill Education, 2015.

[figure not shown]
[figure not shown]

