- For all continuous data except the haematological parameters, box plots of the change from baseline over time, by dose group (Part 1), including a horizontal reference line at zero
- For haematological parameters, box plots of the absolute values over time, by dose group (Part 1), including a horizontal reference line at zero

To enable assessment of the potential for drug-induced liver injury, for all study parts the following outputs will be produced:

- A scatter plot of maximum on-treatment alanine aminotransferase (ALT) versus maximum on-treatment total bilirubin (x-axis), both expressed as multiples of the ULN, including reference lines at $3 \times \text{ULN}$ for ALT, and $2 \times \text{ULN}$ for total bilirubin. For each patient, the maximum ALT and maximum total bilirubin may occur at different visits
- A scatter plot of maximum on-treatment aspartate aminotransferase (AST) versus maximum on-treatment total bilirubin (x-axis), both expressed as multiples of the ULN, including reference lines at $3 \times \text{ULN}$ for AST, and $2 \times \text{ULN}$ for total bilirubin. For each patient, the maximum AST and maximum total bilirubin may occur at different visits.

In the event that the scatter plots of ALT or AST against bilirubin identify any potential Hy's law cases (patients with either both $\text{ALT} > 3 \times \text{ULN}$ and total bilirubin $> 2 \times \text{ULN}$, or both $\text{AST} > 3 \times \text{ULN}$ and total bilirubin $> 2 \times \text{ULN}$), profile plots over time will be produced for these patient's liver function tests (ALT, AST, ALP and total bilirubin), expressed in multiples of the ULN, showing all four FLT parameters on the same plot.

Physical examination data will be listed.

To further assess the tolerability of ASLAN003, dose intensity and treatment exposure, as defined in Section 3.2.2, will be listed and summarized by treatment arm. Dose intensity and exposure summaries will be presented by cycle for the first 3 cycles, and overall.

Swimmer plots of the time on treatment will be presented for all patients in the EFR set. The bars on these plots will be ordered as follows:

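### Protocol Table 2 keeps a Grade 3 ALT/AST, Child-Pugh Class A patient on drug for at least another week even when concurrent bilirubin meets the SAP's potential Hy's law thresholds

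*Protocol*

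**What the plan says.** Protocol 5.3 sets a general rule: for a Grade 3 or worse "toxicity attributed to ASLAN003 by the investigator, the study drug should be interrupted", with discretion to continue for disease-related cytopenias and similar events. AST, ALT and GGT are handled separately. For Grade 3 or worse elevations of these enzymes, "interruption of study drug is based on the assessment of Child-Pugh score", as set out in Table 2.

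The Grade 3 part of Table 2 works as follows:

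- Class A: "Class A: Reduce dose by 50 mg for 1 week then reassess".
- At reassessment, Class A and "still G3: Reduce dose by 50 mg". At Grade 2 the current dose is kept, and at Grade 1 or less the last higher dose is resumed.
- Class B or worse: interrupt until Grade 1 or less.

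Grade 4 is interrupted in every class. Appendix 3 sets the classes: "Class A: 5-6 points Class B: 7-9 points".

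SAP 7.7.1 defines a potential Hy's law case as ALT or AST above 3 x ULN together with total bilirubin above 2 x ULN. It uses the definition for display: "In the event that the scatter plots of ALT or AST against bilirubin identify any potential" cases, liver-test profile plots are drawn for those patients.

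**The concern.** A transaminase rise accompanied by a bilirubin rise is the pattern the SAP itself singles out when it looks for drug-induced liver injury. The dosing table does not look for that pattern. It looks at Child-Pugh class, in which bilirubin is one of five items and can be raised without the patient leaving Class A.

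A patient can therefore show the SAP's pattern at a single visit and be told to continue at a lower dose, while most other attributed Grade 3 toxicities are interrupted at once. Protocol 1.4 describes liver-test elevation as a probable class effect to which elderly subjects may be more susceptible, so the gap concerns the toxicity the protocol most expects. The 28-day withdrawal rule, "If study drug is interrupted for continuous 28 days due to AE, the patient must be withdrawn from the study drug", gives no protection here, because it counts interrupted days and the Class A row creates none.

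**Working it through.** The plan states no figure to reproduce. The check has three steps.

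**1. Highest bilirubin compatible with Class A (Appendix 3).** Bilirubin scores 1 point below 2 mg/dL, 2 points at 2-3 mg/dL and 3 points above 3 mg/dL. Albumin, INR, ascites and encephalopathy score 1 to 3 points each, giving 3^4 = 81 combinations of the other four items.

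- Bilirubin 2-3 mg/dL: minimum total 2 + 4 x 1 = 6, Class A. Only 1 of the 81 combinations (all four at 1 point) stays in Class A. One extra point gives 7, Class B.
- Bilirubin above 3 mg/dL: minimum total 3 + 4 x 1 = 7, Class B.

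So 3.0 mg/dL is the ceiling for Class A.

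**2. Overlap with the SAP threshold.** The overlap is bilirubin above 2 x ULN and no higher than 3.0 mg/dL, so its width is 3.0 - 2 x ULN. The documents give no bilirubin ULN (Protocol 6.3.1.12 uses local laboratories), so a range is assumed:

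| Assumed ULN (mg/dL) | 2 x ULN | Range that is Class A and above 2 x ULN | Width |
|---|---|---|---|
| 0.8 | 1.6 | >1.6 to 3.0 | 1.4 |
| 1.0 | 2.0 | >2.0 to 3.0 | 1.0 |
| 1.2 | 2.4 | >2.4 to 3.0 | 0.6 |
| 1.4 | 2.8 | >2.8 to 3.0 | 0.2 |
| 1.5 or more | 3.0 or more | none | 0 |

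The enzyme half of the definition needs ALT or AST above 3 x ULN. The protocol grades by CTCAE 4.03 without printing cut-offs, so it is assumed that Grade 3 ALT/AST lies above that level. An isolated Grade 3 GGT does not qualify. Entry requires bilirubin, AST and ALT no higher than 1.5 x ULN (Protocol 4.1), so an eligible patient in this range has worsened since screening.

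**3. Drug taken before the first reassessment.** From the full cohort dose, with the 50 mg step read per administration, the amount is 7 days x administrations per day x (dose - 50 mg):

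- 100 mg QD: 7 x 1 x 50 = 350 mg
- 200 mg QD: 7 x 1 x 150 = 1050 mg
- 100 mg BID: 7 x 2 x 50 = 700 mg
- 200 mg BID: 7 x 2 x 150 = 2100 mg

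Interruption would give 0 mg. If the step is instead read per day, the BID figures become 7 x (200 - 50) = 1050 mg and 7 x (400 - 50) = 2450 mg. Either way, the first action is continued dosing.

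**The case against.** **The SAP definition is a retrospective screen.** It uses each patient's maxima, which may fall at different visits, and nothing in either document makes it a stopping criterion. That stands: a patient flagged in the scatter plots was not necessarily mishandled under Table 2. The point is limited to both values being raised together, and it uses the SAP's thresholds without claiming that the SAP requires a stop.

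**The window is narrow.** It needs a low enough ULN and a bilirubin inside a band 0.6-1.0 mg/dL wide (at ULN 1.0-1.2). At bilirubin 2-3 mg/dL it also needs four normal companion items; albumin of 2.8-3.5 g/dL alone gives Class B and interruption. This stands too, and the documents do not allow a frequency to be estimated. Bilirubin is also outside the enzyme exception, so an attributed bilirubin rise that itself reached Grade 3 would be interrupted under the general rule.

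**Other safeguards exist.** Protocol 1.5 asks for liver monitoring, 6.3.1.12 recalls patients with a significant laboratory shift within 2 weeks, 4.3 has the investigator withdraw a patient whose interest is not served by continuing, and the steering committee oversees safety. These are monitoring, discretion or cohort-level oversight. None changes what Table 2 directs for the individual patient.

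**Reduction may be deliberate.** Protocol 1.3.4 describes the enzyme elevation as transient and the hepatocyte effect as reversible, and 1.4 reports multiple doses up to 400 mg as well tolerated in healthy subjects. That can justify reducing the dose for an isolated enzyme rise. It does not address a combined rise with bilirubin.

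**Conclusion.** The gap is real and narrow. For concurrent Grade 3 ALT or AST and bilirubin above 2 x ULN but no higher than 3.0 mg/dL in a Class A patient, Table 2 directs a 50 mg reduction and at least one more week of drug (350 to 2100 mg, by cohort), with interruption left to the investigator. This rests on a local bilirubin ULN below 1.5 mg/dL, Grade 3 ALT/AST lying above 3 x ULN, and the bilirubin rise not itself reaching Grade 3.

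A reader might go further in two ways that the documents do not support.

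- **Drug continues for several weeks until the steps reach zero.** That happens only if the patient stays Grade 3 and Class A at every reassessment. Grade 4 or Class B leads to interruption, so only the first week follows from the table.
- **The earlier study of 100 mg QD in healthy elderly subjects shows the retained dose to be unsafe.** Protocol 1.4 reports "Only 1 subject completed 14 days of QD dosing" but gives no reason for the early stops, so that result cannot carry the argument.

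**What to change.** Add a first row to Table 2, above the Grade 3 and Grade 4 rows:

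> ALT or AST > 3 x ULN with concurrent total bilirubin > 2 x ULN (same sample or same visit), any Child-Pugh class: interrupt until ALT, AST and bilirubin are <= G1; the 28-day withdrawal rule applies; resume only at a reduced dose, and withdraw if the patient is already at 50 mg per administration.

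Requiring bilirubin to settle as well matters because the existing reassessment row returns a Class A patient to the last higher dose on enzyme grade alone. The exit at 50 mg is needed because Protocol 5.1 supplies 50 mg capsules and no lower dose is defined.

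The cost is one table row. ALT, AST and bilirubin are already scheduled at every treatment visit. The row does not need INR, which Protocol Table 1 schedules only at Screening, Cycle 1 Day 15 and EOT. The SAP needs no change, since the thresholds are its own. The downside is that the row acts whatever the cause and may act below Grade 3, so a few patients whose combined rise comes from disease or sepsis will have a short interruption.

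Whether the 50 mg step applies per administration or per day on BID dosing, and whether 50 mg is the floor in the existing rows, should be clarified separately.

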5.4 Intra-patient dose escalation

Intra-patient dose escalation is allowed when the patient has no ongoing study drug-related AE, and all patients in the cohort of targeted dose have completed at least one cycle of treatment without unexpected safety issue identified. Prior agreement with ASLAN Pharmaceuticals would need to be obtained for the dose escalation.

5.5 Packaging, Labeling and Storage

Study drug will be packaged and labelled by the Sponsor according to all local regulatory requirements. Study drugs are packaged in aluminum foil blisters in 2 × 3 format. Blisters are further packaged using either fibreboard cartons or wallets to facilitate clinical use.

Study centers and pharmacies are to store ASLAN003 under controlled conditions 15°C -25°C. Upon dispensing to patients, study drug may be stored up to 30°C or in a fridge 2-8°C. The storage area of the study center, must be a secure, temperature controlled, locked environment with restricted access. Study centers will be required to keep a temperature log to establish a record of compliance with these storage conditions.

Accurate records must be kept regarding dispensing and return of the study drug for each individual patient in the study. Reasons for deviating from the expected dispensing or return of the study drug must be recorded.

No special procedures for the safe handling of ASLAN003 are required. The Sponsor will be permitted upon request to audit the supplies, storage, dispensing procedures and records.

5.6 Blinding

Part 1 is a single-arm, dose optimizing, non-randomized study. Hence, blinding is not applicable.

Part 2 is an open label, single arm design. All patients in Part 2 will receive the same treatment and dose, thus blinding is not applicable for Part 2.

5.7 Study Drug Accountability

The Investigator is responsible for maintaining accurate study drug accountability records throughout the study.

Each dispensing of the study drug will be documented in the eCRF.

The Investigator is responsible for returning all unused or partially used study drug to the Sponsor and must verify that all the unused or partially used drug supplies have been returned by the patient and that no remaining supplies are in the Investigator's possession.

